2.2 Deviations

The study team and study physician/study clinical lead will review protocol deviations as recorded during the conduct of the study to assess whether these deviations are considered to impact the completeness, accuracy, and/or reliability of the study data or to significantly affect a patient's rights, safety, or wellbeing thus being deemed important. At a minimum, important protocol deviations may include:

- Patients who entered the study even though they did not fulfil the eligibility criteria.
- Patients who developed study treatment administration discontinuation criteria but continued with study treatment administration.
- Patients who received the wrong study treatment or incorrect dose.
- Patients who received a disallowed concomitant medication.
- Patients with other important protocol deviations determined in part by study design, the critical procedures, study data, patient protections described in the protocol, and the planned analyses of the study data, including those protocol deviations related to coronavirus disease 2019 (COVID-19)

This list is not intended to be exhaustive. Other factors/protocol deviations may be identified at any time and through various sources by the study team. Based on the latest version of the study-specific protocol deviations management plan, identified deviations, as included in the cumulative clinical trial management system (CTMS) report, will be reviewed by the study team and study physician/study clinical lead monthly and will be considered in the final evaluation of patient evaluability for inclusion in the relevant analysis sets. Details will be provided in a separate study-specific protocol deviations and reasons for exclusion specifications plan.

Prior to database lock and subsequent routine study unblinding, decisions on patient evaluability, assignment to the various analysis sets (with the exception of the PK analysis set finalised after routine study unblinding only) and identified important protocol deviations for

presentation purposes will be finalised in cross-functional collaboration between AstraZeneca and IQVIA.

3 PRIMARY AND SECONDARY VARIABLES

3.1 General Principles

3.1.1 Missing Data

In general, and unless specifically detailed in subsequent sections, variables will be analysed and/or summarised using available data only. Missing data will not be imputed.

Sensitivity analysis of the primary outcome to account for missing data will be performed. The data handling rules for these sensitivity analyses can be found in [Appendix E Accounting for Missing Data](#).

For the handling of missing/partial start and stop dates of medications and therapies, including blood product transfusions, refer to [Appendix C Missing/Partial Start and Stop Dates for Medications/Transfusions](#).

Similarly, for the handling of missing/partial date of birth, SCD diagnosis dates and for prior VOC events start and stop dates as captured on the VOC electronic case report form (eCRF), refer to [Appendix D Missing/Partial Dates for Date of Birth, Diagnosis of Sickle Cell Disease, and Prior VOCs, and VOCs During the Study](#).

3.1.2 Baseline

Baseline is the last assessment collected (scheduled or unscheduled) prior to the first dose of study treatment, or last assessment collected prior to or at randomisation (Visit 2), for patients who are randomised but do not receive any study treatment. For in-clinic assessments with an assessment date equal to the first dose of study treatment, the assessment will be assumed to be pre-dose since all assessments are to be done prior to dispensing study treatment according to the protocol. For adverse events (AEs) and concomitant medications with start date equal to the first dose of study treatment, the event will be considered post-baseline.

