- j Electronic recording of worst pain according to FPS-R/FLACC and localisation of pain after experiencing a VOC, analgesic use and absence from school/work due to SCD.
- k The HRQL (PedsQL) instruments are patient-reported if 5-7 years, 8-12 years, or 13-18 years and reported by a caregiver if the patient is ≤ 4 years.
- l Morning dose of IP to be taken at the site. The palatability/swallowability questionnaire assessed by an observer in children ≤ 4 years, and by Facial Hedonic Scale (FHS) for children ≥ 5 years.
- m Samples for PK and PD analysis will be taken 0 hour (predose) and 2 hours postdose at specified visits and in case of changed dose due to weight increase. No predose PK sample at Visit 2.
- n SAEs should be collected from when the ICF is signed. AEs should be collected from time of randomisation.

Note: In case of modified follow-up when IP is discontinued, the study site visits can be replaced with telephone contact visits as per [Table 3](#).

Table 3 Schedule of Assessments - Telephone visits during treatment period

	Treatment period ^a								For details see Protocol Section
Visit Number	5	7, 8	10, 11	13, 14	16, 17	19, 20	22, 23	25, 26	
Month	2	4, 5	7, 8	10, 11	13, 14	16, 17	19, 20	22, 23	
Visit Window	±7 d	±7 d	±7 d	±7 d	±7 d	±7 d	±7 d	±7 d	
Reminder of eDevice use and ensure data collection of potential VOC events ^b	X	X	X	X	X	X	X	X	5.1.1
Concomitant medications	X	X	X	X	X	X	X	X	7.7
Adverse event collection (AEs and SAEs)	X	X	X	X	X	X	X	X	6

AE Adverse event; d Day; eDevice Electronic device; FLACC Face, Legs, Activity, Cry, Consolability Scale; FPS-R Faces Pain Scale-revised SAE Serious adverse event; VOC Vaso-occlusive crisis.

^a See [Appendix E](#), a Guide for Scheduled Telephone Visits.

^b Electronic recording of pain according to FPS-R/FLACC when experiencing a VOC, analgesic use and absence from school/work due to SCD.

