5.5.2 Collection of samples

Blood samples for determination of platelet aggregation in whole blood will be taken at the time presented in [Table 2](#). Except for the important PD sample taken prior to first dose of study drug at Visit 2 randomisation where no PK sample is taken, the collection of PD samples are thereafter matched with PK samples. To maintain the blinding of treatment allocation, the PD results will not be available to the site, and individual PD results will not be available to the Sponsor.

The time of last dose intake prior to any VASP visits (ie, the evening dose the day before the visit) needs also to be precisely recorded in the eCRF to be able to relate the predose VASP inhibition to time after ticagrelor dose intake.

The predose VASP sample also contains important information on the relationship of ticagrelor dose to exposure and platelet inhibition response and therefore, the correct time recording of the last dose the evening before the visit is equally important as the sample itself.

In case of increased dose due to increased weight, the PD sample will be collected at the following visit. The PD sample will be collected 0 hours (predose) and 2 hours postdose.

Samples will be collected and labelled as detailed in the Laboratory Manual.

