5.6 Genetics (Not applicable)

5.7 Biomarker analysis (Not applicable)

5.8 Volume of blood

The total maximum volume of blood that will be drawn from each patient at each study visit is listed in Table 5 below.

Table 5 Volume of blood to be withdrawn from each patient

	Total maximum volume (mL)	
	12 to 24 kg body weight	>24kg body weight
Visit 1 (Enrolment)	9,9	13,8
Visit 2 (Randomisation)	6,6	7,7
Visit 3 (2 weeks)	3,4	4,5
Visit 4 (4 weeks)	7,8	8,9
Visit 6 (3 months)	0	0
Visit 9 (6 months)	7,8	8,9
Visit 12 (9 months)	0	0
Visit 15 (12 months)	7,8	8,9
Visit 18 (15 months)	0	0
Visit 21 (18 months)	7,8	8,9
Visit 24 (21 months)	0	0

Table 5 Volume of blood to be withdrawn from each patient

	Total maximum volume (mL)	
	12 to 24 kg body weight	>24kg body weight
End of Study (EOS)	7,8	8,9
Follow Up Visit	3,4	4,5
Total (mL)	62,3	75

Note: Visits 5, 7, 8, 10, 11, 13, 14, 16, 17, 19, 20, 22, 23, 25 and 26 are telephone visits.

Note: blood volumes are applicable to central laboratory only; local laboratory practices may vary, however the maximum volume should not exceed those recommended in the appropriate local guideline.

*Maximum volume during 30 days: 19,9 mL ** Maximum volume during 30 days: 26 mL

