7.2.1 Treatment during double-blind randomisation period

Randomisation to twice daily double-blind treatment with ticagrelor or placebo will occur at Visit 2 via the IXRS. Eligible patients will be randomly assigned to 1 of 2 treatment regimens, based on body weight at Visit 2:

- ≥ 12 to ≤ 24 kg body weight: 15 mg - 1 tablet of ticagrelor 15mg or 1 tablet of placebo to match ticagrelor 15 mg twice daily
- > 24 to ≤ 48 kg body weight: 30 mg - 2 tablets of ticagrelor 15mg or 2 tablets of placebo to match ticagrelor 15mg twice daily
- > 48 kg body weight: 45 mg - 3 tablets of ticagrelor 15mg or 3 tablets of placebo to match ticagrelor 15mg twice daily

At Visit 2, the first dose of IP will be administered at the clinic by site staff as soon as possible after randomisation and after all baseline assessments have been completed. Subsequent doses should be taken morning and evening, at approximately 12-hour intervals. Missed doses of ticagrelor or placebo blinded IP should not be compensated (ie, if a dose is missed the next regularly scheduled dose should be taken and should not be doubled).

The study drug will be administered orally either swallowed whole or dispersed in water, other suitable liquids or vehicles based on age and/or ability to swallow study drugs. Refer to handling instructions for further details.

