Pharmacokinetics (PK) analysis set	
All randomised patients who receive at least one dose of ticagrelor and provide at least one post-dose analysable plasma sample for PK analysis will be included in the PK analysis set.
 
Patients with important protocol deviations including changes to the procedures that may impact the quality of the data, or any circumstances that can alter the evaluation of the PK analysis may be excluded from the PK analysis set.

Pharmacodynamics (PD) analysis set	
All patients who receive at least one dose of randomised study treatment, ticagrelor or placebo, and who provide at least baseline and one post-baseline (pre-dose and/or post-dose) analysable sample will be included in the PD analysis.
 
Patients with important protocol deviations including changes to the procedures that may impact the quality of the data, or any circumstances that can alter the PD evaluation may be excluded from the PD analysis set.

Table 2 Summary of Outcome Variables and Analysis Sets

Variable	Analysis Set
Baseline data	
Disposition	All patients

Variable	Analysis Set
Important protocol deviations	Full analysis set
Analysis sets	All patients randomised
Demography and baseline characteristics, medical history, disease characteristics, etc.	Full analysis set
Efficacy data	
Vaso-occlusive crises (VOCs) ^a	Full analysis set
Painful crises	Full analysis set
Acute chest syndromes (ACSs)	Full analysis set
Acute sickle cell disease (SCD) complications	Full analysis set
Health-related quality of life (HRQL)	Full analysis set
Absence from school/work due to SCD	Full analysis set
Pain intensity during VOCs	Full analysis set
Analgesics use during VOCs	Full analysis set
Duration of painful crises	Full analysis set
Duration of ACS	Full analysis set
VOCs requiring hospitalisation or emergency department visits	Full analysis set
Days hospitalised for VOC	Full analysis set
Days hospitalised for acute SCD complications	Full analysis set
Swallowability and palatability	Safety analysis set
SCD-related red blood cell transfusions	Full analysis set
Safety data	
Adverse events ^b	Safety analysis set
Bleeding events	Safety analysis set
Concomitant medications, procedures, and therapies	Safety analysis set
Laboratory measurements	Safety analysis set
Physical examinations	Safety analysis set
Electrocardiograms (ECGs)	Safety analysis set
Vital signs	Safety analysis set
Overdoses	Safety analysis set
Exposure	Safety analysis set

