3.5.3 Pharmacodynamic Variables

The pharmacodynamic variable which addresses the PD properties of ticagrelor, as inhibitor of platelet aggregation, is the Platelet Reactivity Index (PRI [%]) measured by vasodilator-stimulated phosphoprotein (VASP) assay.

The PD samples will be collected at 0 hours (pre-dose) and 2 hours post-dose as per schedule of assessments (refer to Table 2 of the latest version of the CSP).

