4.2.10.3 Pharmacodynamic Variable

Pharmacodynamic analysis, by actual treatment group, will be performed utilising patients considered evaluable for inclusion in the PD analysis set and who provide at least baseline and one post-baseline (pre-dose and/or post-dose) analysable sample (refer to Section 2.1).

All available data will be listed for the safety analysis set with any PD data to be excluded from the summary tables and figures indicated by means of a flag.

PRI (%) values will be presented by actual study treatment received for each week/month and timepoints (pre-dose and 2 hours post-dose). Descriptive statistics will be presented for each observed result including:

- gMean: Calculated as $\exp[\mu]$, where μ is the mean of the data on a natural logarithmic scale
- gSD: Calculated as $\exp[s]$, where s is the SD of the data on a natural logarithmic scale
- gCV%: Calculated as $100 \sqrt{[\exp(s^2)-1]}$, where s is the SD of the data on a natural logarithmic scale
- aMean
- SD
- Median
- Minimum (min)
- Maximum (max)

and for change from baseline (refer to Section 3.1.3) by means of:

- aMean
- SD
- Median
- Minimum (min)
- Maximum (max)

In addition, PRI (%) will be presented graphically as follows:

- Individual patient PRI-time spaghetti plots for the pooled weight-bands/doses and for each weight-band/dose level. Pre-dose and 2-hours post-dose PRI values will not be averaged and will be presented separately.
- Mean (geometric and arithmetic) pre-dose PRI values versus visit (visit number as X-axis) for the pooled weight-bands/dose level and for each weight-band/dose level.
- Mean (geometric and arithmetic) 2-hours post-dose PRI values versus visit (visit number as X-axis) for the pooled weight-bands/dose level and for each weight-band/dose level.

If considered relevant, the same data handling conventions detailed for the PK analyses will be applied for those PRI (%) values that are NQ, NR or NS.

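### The same-day baseline rule in SAP 3.1.2 treats the Visit 2 two-hour post-dose PRI sample as pre-dose and, read literally, makes it the PRI baseline

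*SAP*

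**What the plan says.** SAP 3.1.2 first defines baseline as the last assessment collected before the first dose. It then adds a rule for the day of the first dose: "For in-clinic assessments with an assessment date equal to the first dose of study treatment, the assessment will be assumed to be pre-dose". The justification is that the protocol has all assessments done before study drug is dispensed. The rule looks only at the date and makes no exception for samples with a scheduled time.

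For PRI, SAP 3.5.3 states: "The PD samples will be collected at 0 hours (pre-dose) and 2 hours post-dose as per schedule of assessments". Protocol Table 2 marks PD sampling at Visit 2, and its footnote m reads: "Samples for PK and PD analysis will be taken 0 hour (predose) and 2 hours postdose at specified visits". The same footnote omits one sample at Visit 2, the pre-dose PK sample; no PD sample is omitted.

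SAP 4.2.10.3 summarises observed PRI separately for the pre-dose and two-hour timepoints. For change from baseline it refers to SAP 3.1.3, which uses the general baseline. No PD-specific baseline is defined. The PD analysis set in SAP Table 1 takes patients "who provide at least baseline and one post-baseline (pre-dose and/or post-dose) analysable sample will be included in the PD analysis", without saying which Visit 2 sample is the baseline.

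**The concern.** The premise of the same-day rule fails for any measurement planned after the first dose at Visit 2. The two-hour PRI sample is one. The palatability assessment, which Protocol 4.2.1 places after the first dose, is another, although no change from baseline depends on it.

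For PRI the failure has a consequence. Both Visit 2 samples carry the date of the first dose, so the rule labels both pre-dose, and the last-assessment criterion then selects the later one. In the ticagrelor arm that value already reflects inhibition by the drug. Change from baseline would then compare drug with drug, and platelet inhibition would be understated in that arm only.

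Membership of the PD analysis set can shift too. A patient whose only PRI samples are the two at Visit 2 would have no post-baseline sample and would drop out of the set, although the two-hour sample is post-dose. A patient with only the two-hour sample would acquire an on-drug baseline.

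PRI is exploratory, but Protocol 1.2.2 chose the doses to inhibit platelets more than prasugrel did, and Protocol 1.5.2 sets a target of 35% to 80%. PRI change from baseline is the planned summary closest to showing whether that was reached.

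**Working it through.** **1. Is a two-hour PRI sample planned at Visit 2?**

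- Protocol Table 2, footnote m: samples at 0 and 2 hours; only the pre-dose PK sample is dropped at Visit 2.
- Protocol 5.4.1: the Visit 2 PK sample is therefore the two-hour one, and PK and PD samples are to be time matched.
- Protocol 5.5.2 describes PD samples as matched to PK samples with one exception: "Except for the important PD sample taken prior to first dose of study drug at Visit 2 randomisation". The two-hour PK sample at Visit 2 thus has a PRI partner.

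**2. Check against the blood volumes in Protocol 5.8, Table 5** (12 to 24 kg / above 24 kg)

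Inputs: Visit 2, 6.6 / 7.7 mL; Visit 3 (safety laboratory only), 3.4 / 4.5 mL; Visit 4 (safety laboratory, two PK and two PD), 7.8 / 8.9 mL. Assumption: the safety laboratory volume at Visits 2 and 4 equals that at Visit 3. The Follow-up Visit, also without PK or PD, has the same 3.4 / 4.5 mL.

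- Visit 4 − Visit 3: 7.8 − 3.4 = 8.9 − 4.5 = 4.4 mL = 2 PK + 2 PD, so PK + PD = 2.2 mL.
- Visit 2 − Visit 3: 6.6 − 3.4 = 7.7 − 4.5 = 3.2 mL.
- If Visit 2 has one PK and two PD draws: PD = 3.2 − 2.2 = 1.0 mL and PK = 2.2 − 1.0 = 1.2 mL. This reproduces the listed 6.6 / 7.7 mL.
- With the same draw sizes and only one PD draw, Visit 2 would be 3.4 + 2.2 = 5.6 mL and 4.5 + 2.2 = 6.7 mL, 1.0 mL below the listed values.

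The volumes fit two PRI samples at Visit 2.

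**3. Effect on change from baseline**

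Let B be the true 0-hour PRI, f the fractional inhibition two hours after the first dose, and I the inhibition at a later sample.

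- Correct change: (1 − I)B − B = −I·B.
- Change under the literal rule: (1 − I)B − (1 − f)B = (f − I)B.
- Error: (f − I)B − (−I·B) = +f·B, at every later visit and timepoint on ticagrelor, and about 0 on placebo.

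The documents give neither B nor f. To show scale only, take I from the HESTIA2 45 mg bd figures in Protocol 1.2.2 (48% before the morning dose, 81% at two hours, after one week). These are PRU values in young adults; carrying them over to PRI in children is an assumption. The range for f is also assumed.

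| f | Pre-dose change, % of B (true −48) | Two-hour change, % of B (true −81) |
|---|---|---|
| 20% | −28 | −61 |
| 35% | −13 | −46 |
| 48% | 0 | −33 |
| 65% | +17 | −16 |

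If percentage change under SAP 3.1.3 were also derived, the wrong value would be the denominator as well. At f = 35%, a true 48% pre-dose inhibition would read 1 − 0.52/0.65 = 20%.

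**The case against.** The best defence is that the literal reading contradicts the paragraph it comes from. The definition in 3.1.2 opens with the requirement that the assessment precede the first dose. The same-day sentence can be seen as a fallback for records whose date cannot show the order, and a sample labelled two hours post-dose needs no such fallback. The protocol also shows which sample is meant: section 5.5.2 singles out the one taken before the first dose, and section 7.2.1 has the first dose given "as soon as possible after randomisation and after all baseline assessments have been completed". A sensible programmer would probably choose the 0-hour sample. An on-drug baseline might also be noticed in review, because observed PRI by timepoint is tabulated regardless.

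Most of this stands as evidence of intent. It does not remove the problem. None of these texts exempts timed samples from the same-day rule, and Protocol 8.5, which takes the closest observation up to and including the randomisation visit, does not separate the two samples either. A programmer who applies the SAP rule as written gets the wrong baseline, and one who follows the opening definition gets the right one.

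It is also fair to say that the sizes shown are illustrations. Only the form of the error, +f·B, follows from the rule itself.

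**Conclusion.** The concern holds. The premise of the same-day rule is false for the Visit 2 two-hour PRI sample, and the rule applied as written gives an on-drug baseline. The error is +f·B on every later PRI change in the ticagrelor arm, so inhibition is understated in proportion to how much the first dose inhibits platelets at two hours. The table's figures rest on an assumed f and on PRU results from another study.

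The scope is limited. PRI change from baseline is an exploratory, descriptive output. No primary, secondary or safety result depends on it, and observed PRI by visit and timepoint remains correct. The interim PD assessment compares each patient with a baseline value, but the documents do not show that it uses this rule. The point should be corrected before the PD outputs are programmed; it does not threaten the trial's main conclusions.

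**What to change.** In SAP 3.1.2, restrict the same-day assumption to assessments scheduled before dosing, and add:

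> For PK and PD samples, the nominal timepoint (with recorded times where available) determines pre- or post-dose status. Baseline PRI is the Visit 2 0-hour (pre-dose) sample. The Visit 2 2-hour sample is post-baseline, including for the PD analysis set.

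The cost is one or two sentences. SAP 4.2.10.3 already uses the nominal timepoints, so no new data are needed.

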3.1.3 Change and Percentage Change from Baseline

Change from baseline will be calculated as the post-baseline value minus the value at baseline:

- Change from baseline (unit) = (post-baseline value – baseline value)

Percentage change from baseline will be calculated as follows when appropriate:

- Percentage change from baseline (%) = (post-baseline value – baseline value)/baseline value × 100

If either the post-baseline value or the baseline value is missing, then both change from baseline and percentage change from baseline value will be set to missing and no imputation of missing values will be done. If the baseline value is zero, the percentage change will be set to missing.

3.1.4 Treatment Period

The double-blind randomised treatment period comprises of regular scheduled in-clinic visits as well as regularly scheduled telephone visits. The treatment period starts at randomisation (Visit 2) through the end of study (EOS) visit regardless of whether the patient prematurely discontinues study treatment. Refer to Section 3.1.4.1 for details on EOS visit. For patients who prematurely discontinue from study participation within this period, the double-blind randomised treatment period is defined through to the last available visit/assessment date or date of premature study discontinuation, whichever is latest.

3.1.4.1 End of Study Visit

Due to premature termination of the study by the sponsor, AstraZeneca, the end of study (EOS) visit is defined by a common study end date (CSED) corresponding to the date of communication to all investigators to immediately discontinue study treatment administration for all patients still ongoing on study treatment.

